1. ABBREVIATED TERMS AND DEFINITIONS

ADE	Adverse Device Effect
AE	Adverse Event
CIP	Clinical Investigation Plan
CO ₂	Carbon Dioxide
F	French
ga	Gauge
HPVG	Hepatic Venous Pressure Gradient
HV	Hepatic Vein
ICE	Intracardiac Echocardiography
ICU	Intensive Care Unit
IFU	Instructions for Use
IRB	Institutional Review Board
ISO	International Standards Organization
ISO 14155	Clinical Investigation of Medical Devices for Human Subjects - Good clinical practice
MELD	Model for End-Stage Liver Disease
mGy	Milligray
mL	Milliliter
mm Hg	Millimeters of Mercury
MPA	Multipurpose Angiographic
PEEK	Polyether Ether Ketone
PI	Principal Investigator
PTFE	Polytetrafluoroethylene
PV	Portal Vein
PVA	Portal Vein Access
PVPC	Portal Vein Puncture-related Complications
SAE	Serious Adverse Event
TIPS	Transjugular Intrahepatic Portosystemic Shunt
US	United States

3. SYNOPSIS

Protocol SCPVA02	
Title	A Retrospective Study to Assess the Safety and Efficacy of Scorpion for Transjugular Intrahepatic Portosystemic Shunt (TIPS) Procedures
Short title	Achieving Portal Access with Scorpion Post-Approval Study 2 (APASS2)
Protocol Number	SCPVA02
Study Device	
Name	Scorpion® Portal Vein Access Set Scorpion®X Portal Vein Access Set
Intended Use	The Scorpion and Scorpion X Portal Vein Access Sets are intended for transjugular liver access in diagnostic and interventional procedures.
Sponsor	
Name	Argon Medical Devices Inc.
Contact Details	[name] [contact] [contact]
Investigational Sites	
Number of Sites	1 site
Location of Sites	United States (US)
Clinical Study Design	
Design	Retrospective, single center, single arm design.
Objective	To evaluate the safety and effectiveness of Scorpion Portal Vein Access Kits for TIPS procedures with the goal of creating the parenchymal tract for indicated interventional procedures. Safety, effectiveness, and performance data for the Scorpion Portal Vein Access sets will be collected
Hypothesis	No formal statistical hypothesis will be tested
Primary Effectiveness Endpoint	Technical success, which is defined as creation of the parenchymal tract between the hepatic vein and an intrahepatic branch of the portal vein confirmed by portogram (CO ₂ /contrast)
Primary Safety Endpoint	Major complications associated with the device/procedure, which are defined as complications resulting in an unplanned increase in the level of care, prolonged hospitalization, permanent adverse sequelae, or death
Secondary Endpoints	
 • Procedural success defined as successful delivery of the shunt • Device-Related Complications, in the judgment of the Principal Investigator

Exploratory Endpoints 
 • Portal vein access (PVA) time defined as the time from hepatic vein access to portal vein access • Procedure duration defined as the interval from the first jugular access for TIPS creation to removal of catheters from the subject • Fluoroscopy Time • Change in Model for End-Stage Liver Disease (MELD) and Child-Pugh score • Radiation dosage measured in Air kerma (mGy) • Contrast volume used • Length of hospital stay and number of ICU days • Change in hepatic venous pressure gradient (HPVG) 	
Clinical Study Population	
Population	
All patients who underwent a TIPS procedure between February 1, 2022, and February 29, 2024 will be considered for enrollment in the study. Procedural data will be collected from patient medical records through hospital discharge.
 
Each TIPS procedure that was completed using one of the Scorpion Portal Vein Access Kits will be considered as an individual case. Cases that meet all inclusion criteria and do not meet any exclusion criteria will be considered eligible for enrollment.

Inclusion Criteria	
 1. Scorpion or Scorpion X kit introduced into the vasculature as the initial device for portal vein access.
Exclusion Criteria	
 1. TIPS procedure was not initiated and/or no portion of the kit was introduced into the vasculature. 2. Inaccessible medical records.
Statistical Analysis	
Statistical Methodology	
Patient demographics and performance parameters will be summarized with mean, standard deviation, median, and range for continuous variables and with frequencies and percentages for discrete variables. Sub-group analysis will be conducted when sample size permits.

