7.1.2. Secondary Outcomes

- a. Procedural success defined as successful delivery of the shunt
- b. Incidence of procedural complications defined as the total occurrence of complications

8. STUDY DESIGN**8.1. Overview**

The planned sample size is to enroll at least 50 eligible cases at a single center in the United States. Clinical data will be retrospectively collected on eligible cases that underwent attempted TIPS procedures with one of Argon's standard Portal Vein Access Set between February 1, 2022 and February 29, 2024.

The participating center will be identified by a site number, and eligible cases will be sequentially assigned a unique 3-digit study identification (ID) number. The ID number will be a combination of the site number followed by a 2-digit number sequentially assigned based on eligibility (e.g. 101, 102, 103).

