8.2. Eligibility Criteria**8.2.1. Inclusion Criteria**

1. Scorpion or Scorpion X kit introduced into the vasculature as the initial device for portal vein access

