8.2.2. Exclusion Criteria

1. TIPS procedure was not initiated and/or no portion of the kit was introduced into the vasculature
2. Inaccessible medical records

9. STUDY ENDPOINTS**9.1. Primary Endpoints**

The primary effectiveness endpoint is technical success defined as creation of the parenchymal tract between the hepatic vein and an intrahepatic branch of the portal vein and confirmed by portogram (CO₂/contrast).

The primary safety endpoint is a composite of major complications associated with the procedure or study device and defined as complications resulting in an unplanned increase in the level of care, prolonged hospitalization, permanent adverse sequelae, or death.¹⁰

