10.2. Patient Selection

Electronic Medical Records (EMR) will be used to identify patients who underwent a TIPS procedure using Scorpion® Portal Vein Access Set or Scorpion®X Portal Vein Access Set with standard techniques from February 1, 2022, through February 29, 2024, by searching for Current Procedural Terminology (CPT) codes 37182 and 37183 within the study period.

Suitable cases identified during the study period will be evaluated for eligibility. Eligible cases will be assigned a sequential 3-digit number as the case ID. Each TIPS procedure attempt will be considered as an individual case with different case ID. The patient log will be retained at the site and filed with the study records at the conclusion of the study.

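### The synopsis defines a case as a TIPS procedure completed with a Scorpion kit, while 8.1, 10.2 and (in effect) the eligibility criteria count attempts; followed literally, it would drop failed attempts from the denominator

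*Combined protocol and SAP*

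**What the plan says.** The case definition appears in several places, and they do not agree.

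- Synopsis, Clinical Study Population: "Each TIPS procedure that was completed using one of the Scorpion Portal Vein Access Kits will be considered as an individual case". The next sentence reads "Cases that meet all inclusion criteria and do not meet any exclusion criteria will be considered eligible for enrollment", so the case definition acts before eligibility is assessed.
- Section 8.1: "Clinical data will be retrospectively collected on eligible cases that underwent attempted TIPS procedures with one of" the sponsor's standard sets.
- Section 10.2: "Each TIPS procedure attempt will be considered as an individual case with different case ID".
- Inclusion criterion (8.2.1, repeated in the synopsis): "Scorpion or Scorpion X kit introduced into the vasculature as the initial device for portal vein access".
- First exclusion criterion (8.2.2, also repeated in the synopsis): "TIPS procedure was not initiated and/or no portion of the kit was introduced into the vasculature". The only other exclusion is inaccessible records.

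Sections 12.2 and 12.3 enrol and analyse all eligible cases, the latter on an as-treated basis. Technical success (9.1) is "creation of the parenchymal tract between the hepatic vein and an intrahepatic branch of the portal vein and confirmed by portogram". Procedural success (Table 3) is delivery of the shunt. Neither definition names the device.

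**The concern.** The case definition sets the denominator of every reported proportion. If a case must have been completed with the kit, an attempt that was abandoned, or finished with another set, never becomes a case and cannot be counted as a failure. Completion with the kit is close to being the primary effectiveness outcome itself, so selecting on it pushes the success rate towards 100% by construction, apart from cases that lack a confirming portogram.

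Safety is affected too. Section 4.1 says that arterial, biliary and capsular injuries can arise while portal access is being attempted. Complications of removed attempts would not reach the primary safety endpoint.

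This matters because 4.3 says the data are to support an initial CE Mark application and be set against the sponsor's acceptance criteria. The documents do not state which wording prevails.

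**Working it through.** **Step 1. The wordings side by side.** Take an attempt in which a Scorpion kit was introduced first and the procedure was then abandoned.

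- Under 10.2 it is a case, and 8.1 includes it.
- It meets the inclusion criterion and is not excluded: the procedure was initiated and the kit was introduced.
- Under the synopsis sentence it is not a case, so eligibility is never reached.

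A procedure begun with Scorpion and finished with another set behaves the same way. Section 8.2 does not use the word attempt, but it covers attempts in effect. The synopsis repeats those criteria, so it also conflicts with itself.

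**Step 2. Inputs.** The plan has no calculated figure to reproduce: 12.2 anticipates at least 50 cases from a preliminary estimate and sales history. I take n = 50 attempts. The documents give no failure rate, so the number of failures f is assumed. Each failure is taken to be an attempt without a portogram-confirmed tract that was not completed with the kit, and every completed case is taken to have its portogram.

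**Step 3. Technical success.** All attempts: (50 − f)/50. Completed only: (50 − f)/(50 − f). Intervals are exact (Clopper-Pearson) 95%; when all cases succeed, the lower limit is 0.025^(1/n).

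| Assumed f | All attempts | Completed only |
|---|---|---|
| 0 | 50/50 = 100% (92.9 to 100) | 50/50 = 100% (92.9 to 100) |
| 1 | 49/50 = 98.0% (89.4 to 99.9) | 49/49 = 100% (92.7 to 100) |
| 3 | 47/50 = 94.0% (83.5 to 98.7) | 47/47 = 100% (92.5 to 100) |
| 5 | 45/50 = 90.0% (78.2 to 96.7) | 45/45 = 100% (92.1 to 100) |

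The same arithmetic holds for procedural success, with f as the number of attempts in which no shunt was delivered.

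**Step 4. Could the rules differ in practice?** The chance of at least one failure in 50 is 1 − (1 − p)^50. At assumed failure rates p of 2%, 5% and 10% this is 63.6%, 92.3% and 99.5%.

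**Step 5. Which removals bias technical success.** Removing a failure turns x/n into x/(n − 1), which is larger. Removing an attempt abandoned after a confirmed tract turns x/n into (x − 1)/(n − 1), which is never larger: 49/50 = 98.00% becomes 48/49 = 97.96%. Only attempts without a confirmed tract inflate the rate.

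**Step 6. Safety.** Assume 3 failed attempts and 3 major complications. On attempts the rate is 3/50 = 6.0% (1.3 to 16.5). On completed cases it is 3/47 = 6.4%, 2/47 = 4.3%, 1/47 = 2.1% or 0/47 = 0% (0 to 7.5), according to whether 0, 1, 2 or 3 of the complications fell in the removed attempts. The rate can move either way.

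**The case against.** The strongest reply is that the harmful reading is unlikely. The same synopsis entry opens with all patients who underwent TIPS. Excluding procedures that were never initiated would be pointless if only completed ones could be cases. Section 10.3.2 records technical and procedural success for each case, which would be almost constant among completed procedures. Completed may simply mean performed. This stands: the bias is conditional on the synopsis sentence being used to find cases. It does not remove the contradiction in a rule that fixes the denominator of both primary endpoints.

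It may also be said that as-treated in 12.3 settles procedures finished with another set. It is the one phrase that bears on them, but the protocol does not define it for a switch. Counting such a tract as a device failure would be a choice that the documents do not dictate.

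A reader might infer two further things that the documents do not support:

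- **That the search itself misses abandoned attempts.** Section 10.2 finds patients "by searching for Current Procedural Terminology (CPT) codes 37182 and 37183 within the study period" and does not say either way, so no error is shown there.
- **That the earlier Scorpion X series (15 of 15 successes, 4.2) caps failures at 10 in 50.** Its exact lower limit is 0.025^(1/15) = 78.2%, a failure rate of up to 21.8%. At that rate the expected count is 50 × 0.218 = 10.9, and the chance of more than 10 is about 54%. The series neither excludes failures nor caps them.

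**Conclusion.** The synopsis sentence is wrong as written and should be corrected. The contradiction is certain; its effect is conditional on the sentence being followed.

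If it is followed, technical success is biased upward by attempts abandoned without a confirmed tract, and by switched cases if these count as failures. Procedural success is biased upward by attempts with no shunt delivered. On the assumptions above, the gap in technical success is 6 percentage points with 3 failures in 50, 10 points with 5, and nil with none. The failure counts are illustrative, not taken from the documents.

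Three stronger readings go too far:

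- **The study will discard failed attempts.** Sections 8.1, 8.2 and 10.2 point the other way.
- **Every abandoned attempt inflates technical success.** One abandoned after a confirmed tract is a technical success.
- **The complication rate would be lowered.** Events would be lost, but the documents do not say that complications are more frequent in failed attempts, so the direction is unknown.

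**What to change.** - **Synopsis:** replace the sentence with one that defines a case as each TIPS attempt in which a Scorpion or Scorpion X kit was the first portal vein access device to enter the vasculature, whether or not the procedure was completed.
- **12.3:** state that all such eligible attempts form the denominator for technical success, procedural success and complications.
- **Secondary suggestion, switched cases:** add one yes/no item to 10.3.2 for portal access finished with another set. The items listed there and in 10.3 name the Scorpion set or main Argon device used, but no switch. Report technical success with switched cases identified, and state in 12.3, consistently with as-treated, whether a tract made only after a switch counts as success of the device.

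The cost is a few sentences and one chart item; the planned sample size does not change. The reported success rate may be lower. Because the data already exist, the rule should be fixed before outcomes are abstracted.

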4. INTRODUCTION

4.1. Background

Portal hypertension is high blood pressure in the portal vein located in the abdomen. The portal vein returns blood from the digestive system to the liver for the purpose of cleaning and filtering waste from the blood. This condition is the most frequent cause of hospitalization, variceal bleed, liver transplantation, and death in patients with cirrhosis.¹

Elevated pressures in the portal venous system will manifest as abdominal ascites, hepatic hydrothorax, hepatorenal syndrome, portal hypertensive gastropathy and gastro-esophageal varices with or without bleeding, which are markers of decompensation and associated with significant morbidity and mortality.

Transjugular intrahepatic portosystemic shunt (TIPS) is a well-established percutaneous modality for decreasing portal hypertension by creating a shunt through the hepatic parenchyma to connect the hepatic vein to the portal vein. Although the major clinical indications for TIPS include refractory variceal hemorrhage and refractory ascites, the full list of TIPS indications includes:²

1. Uncontrollable variceal hemorrhage
2. Current or prior variceal hemorrhage that is not amenable to initial or continued endoscopic therapy
3. Prophylaxis against recurrent variceal bleed in high-risk patients
4. Portal hypertensive gastropathy
5. Refractory ascites
6. Hepatic hydrothorax
7. Budd-Chiari syndrome
8. Hepatopulmonary syndrome
9. Hepatorenal syndrome
10. Decompression of portosystemic collaterals prior to abdominal surgical procedures

Overall, the TIPS procedure is one of the most challenging procedures performed by interventional radiologists, and the most difficult and time-consuming step in the procedure is accessing the portal vein. Many techniques for accessing the portal vein have been described in literature and they fall into three broad categories:

- Fluoroscopically guided TIPS creation with the use of landmarks or portography (wedged hepatic vein portography with CO₂ umbilical venography)
- Transabdominal ultrasound – guided placement of a portal vein target via transhepatic or transsplenic access to facilitate subsequent fluoroscopically guided access
- Transabdominal intravascular ultrasound (IVUS), or intracardiac echocardiography (ICE) guidance³

ICE uses a low-frequency, side-firing intravascular transducer and is more commonly used for intracardiac procedures. However, in this application it can be used to depict the central portion of the liver, which permits visualization of the needle and the PV target without the use of fluoroscopy or contrast medium.

Cam et al.⁴ reported that ultrasound-guided PV access and percutaneous PV guidewire placement for fluoroscopic targeting during TIPS creation are associated with shorter procedure and fluoroscopic times and potentially decreased complications. Many of the procedure-related complications of TIPS creation, such as arterial injury, biliary injury, and extracapsular puncture may occur during attempted portal vein access. As the number of needle passes for successful PV access increases, so may the potential for puncture-related complications.

Historically, the most performed technique for portal venous access involved wedge hepatic venography with carbon dioxide to visualize the portal vein followed by passing the needle under fluoroscopic guidance. In the last 10 years, imaging guidance options have evolved beyond traditional wedge carbon dioxide portography to include ultrasound-guided options such as transabdominal, intravascular and intracardiac echocardiography to help with visualization and portal vein cannulation. Portal vein access may require multiple needle passes and is considered the riskiest step in TIPS creation with possible incidence of portal vein puncture-related complications (PVPC).⁵ Complications result from inadvertent injury to non-target vessels and include damage to the hepatic artery or extrahepatic portal vein, transcapsular puncture and laceration of the liver capsule, all of which can result in life-threatening hemorrhage.⁶

4.2. Prior Investigations

The Rosch-Uchida and Colapinto sets manufactured by Cook Medical (Bloomington, Indiana, US) are two different needle sets currently available and most encountered. A recent systematic review of literature showed that the overall incidence of PVPC with the Cook sets was 3.6%.⁶ The procedure duration varies in literature due to protocol differences and imaging techniques used. David et al.⁷ reported a mean procedure duration of 86.2 minutes using ultrasound guidance. In a study evaluating time to portal vein access, mean time to portal venous access was statistically significant between conventional fluoroscopy at 46 minutes and intravascular US-guided TIPS at 31 minutes.⁸

In a retrospective study of 15 cases with Scorpion X (Needle model), technical success was achieved in 100% of cases with an average of 2.7 passes, and because of the bi-directional needle, no cases required adjustment to the curvature of the needle.⁹

The APASS prospective study had three cases, but the study was early terminated due to slow enrollment accrual. Two cases were Scorpion, while the remaining one was Cook. Procedural success was achieved in 100% of cases.

4.3. Study Rationale

The aim of this study is to collect real-world data on safety, effectiveness, and performance of the Scorpion Portal Vein Access Sets in subjects who underwent a TIPS procedure. The study supports post-market surveillance and will serve to provide clinical data for the initial CE Mark application.

Findings from this study will provide valuable clinical evidence to ensure that Argon's standard Portal Vein Access Sets are in line with state of the art and our established acceptance criteria for safety and performance when used as intended.

5. DEVICE DESCRIPTION AND INTENDED USE

5.1. General Device Description

There are two models of the Scorpion Portal Vein Access Sets: Scorpion and Scorpion X. The Scorpion model has a stylet as the puncture tool and the Scorpion X model has a 17 ga needle as the puncture tool (**Figure 1**).

A. Scorpion Nitinol Stylet

B. Scorpion X Nitinol Needle

FIGURE 1. SCORPION PUNCTURE TOOL CONFIGURATIONS

In addition to the puncture tool, each Scorpion set contains an MPA catheter, a stiffening cannula, a cannula sheath, and a PEEK catheter (see **Table 1**). The Scorpion® Portal Vein Access Set does not contain medicinal substances, human, or animal tissues or their derivatives, or other biologically active substances.

The Scorpion set is used to gain access to the hepatic vein and guide the puncture tool (stylet or needle) through the liver parenchyma. The puncture tool makes a pathway between the hepatic vein and the portal vein. The choice of stylet or needle is physician preference based on training and the subject case. This will not have an impact on the endpoints of this clinical study and, as such, there is no requirement that the same number of both models is used during the study.

The Scorpion set is compatible with the 10F Flexor® Check-Flo® Introducer Set manufactured by Cook Medical and is typically in use up to four hours.

Table 1. Components of the Scorpion Sets

Scorpion	Scorpion X	Function / Description
0.040" Nitinol Stylet	17ga Nitinol Needle	
5F PEEK Catheter	6.2F PEEK Catheter	The stylet/needle and PEEK catheter assembly is used to navigate the liver parenchyma and make a pathway from the hepatic vein to the portal vein.
Spacer Clip	Spacer Clip	The spacer clip is placed between the PEEK Catheter and the stylet/needle when assembled to prevent premature puncture prior to proper orientation with the portal vein.
5F MPA Catheter	5F MPA Catheter	The MPA catheter is used for angiographic procedures to deliver radiopaque media.
14ga Stiffening Cannula	13ga Stiffening Cannula	
7F Cannula Sheath	8F Cannula Sheath	The cannula and cannula sheath assembly is used for bi-directional steering through the liver parenchyma into the hepatic vein to orient toward the portal vein.

MPA = Multipurpose Angiographic

5.2. Indications for Use

The Scorpion Portal Vein Access Sets are intended for transjugular liver access in diagnostic and interventional procedures.

5.3. Device Identification and Tracking

As commercially available devices, Scorpion® Portal Vein Access Set and Scorpion®X Portal Vein Access Set were obtained by the site through normal commercial procurement methods and stored and accounted for following site-specific policies.

